
**Vitamin D status: current knowledge**

There are 3 sources of vitamin D: endogenous production in skin upon absorption of ultraviolet (UV) B (290-315 nm) radiation, vitamin D in foods and finally dietary supplements. Since a standard western diet contains only very few food components, which contain vitamin D (fatty fish and liver extracts) our most important source of vitamin D is endogenous conversion of 7-dehydrocholesterol (7-DHC) to previtamin D3 by UVB, which isomerizes to vitamin D3 by thermal energy. However, this vitamin D synthesis is only reliably available year-round at latitudes between 40 ° north and 40 ° south, indicating that in our regions the required levels of UVB are low or non-existent for a significant proportion of the year. Data indicate that indeed insufficient vitamin D levels are widespread both in the American and European population (Holick 2006; Lee 2009; Adams 2010,) especially in wintertime (Rhodes 2010).

Vitamin D (from the food, via supplements or produced by UVB in the skin) is biologically inert and the biological effect of vitamin D results only as a consequence of its sequential metabolism in the liver into 25-hydroxy-vitamin D3 (25(OH)D3) and then in the kidney into the steroid hormone, 1alpha,25-dihydroxyvitamin D3 (1,25(OH)2D3). The classical signaling pathway of 1,25(OH)2D3 employs the vitamin D receptor (VDR), which is a transcription factor for 1,25(OH)2D3 target genes, including the cyclin dependent kinase inhibitors, p21 and p27.

Vitamin D receptor (VDR) is believed to be located in the nucleus prior to activation by 25(OH)2D3, which dissociates from the serum vitamin D-binding protein, enters the cell by diffusion and binds the VDR. Ligand binding produces conformational changes, resulting in dimerization, necessary for high affinity interaction with target gene promoter at the vitamin D response element (Osborne, 2002).

The gene encoding VDR maps to the chromosomal region 12q13 and contains numerous common variants, that are hypothesized to influence the function and or expression of VDR (Egan 2009).

It is generally agreed that the serum concentration of 25(OH)D3 in normal subjects is the best indicator for vitamin D status and currently a serum concentration below 10 ng/ml (<25/ nmol/L) is considered as vitamin D deficient, and a serum concentration below 20 ng/ml (< 50 nmol/L) as vitamin D insufficient. The optimal level for health is believed to be reached at 30 ng/ml (75 nmol/L), while some individuals may be at risk for toxicity (hypercalcaemia, vomiting, thirst, polyuria, ectopic calcifications) when their 25(OH)D3 levels are in the range of 100-150 ng/ml (or 250-300 nmol/L). Current recommendation for additional vitamin D intake via supplements, in addition to skin synthesis and nutritional intake is 1000 IU/d. A good safety profile for this amount has been shown in more than 50 000 subjects over a several year treatment period (Norman and Bouillon, 2010), while doses for chemoprevention studies (colon, prostate and breast cancer) range from 2000 to 4000 IU /day (ClinicalTrials.gov). A recent IWT/TBM project investigating the effect of vitamin

D supplementation on Chronic Obstructive Pulmonary Disease (COPD) on 90 patients in a placebo controlled setting, has shown that a single monthly dose of 100 000 IU, given during a year is safe, is able to increase the 25 (OH)D3 levels in serum, from insufficient levels (<20 ng/ml) to 50 ng/ml (Lehouck, 2012). , and has no immunosuppressive effects (personal communication, [name] and [name], UZ KULeuven).

Another important finding is that vitamin D levels are influenced by the genetic variability of every individual. Data from a very recent genome wide association study (Wang 2010) show that the following genes contribute to the variability of serum concentrations of 25(OH)D3: 7-DHC reductase (responsible for the availability of 7-DHC in the skin), the liver 25-hydroxylase CYP2R1 (involved in the conversion of vitamin D into 25-hydroxyvitamin D3) and CYP24A1 (key degradation enzyme). Additionally polymorphisms in GC, the gene encoding vitamin D-binding protein, had the greatest effect on serum 25-hydroxyvitamin D3 concentration.

#### **Vitamin D and melanoma: current knowledge.**

Laboratory data, animal studies, epidemiological observations and clinical studies indicate that Vitamin D may have a preventive effect on melanoma development and may affect tumor progression or melanoma outcome

The VDR has been identified in cultured melanoma cells, in melanoma xenografts and in primary melanoma tissue (reviewed by Osborne 2002 and Egan 2009). Vitamin D metabolites have been shown to inhibit proliferation and induce differentiation in melanoma cell lines. In vivo 1,25 (OH)2 D3 has been shown to suppress growth in human melanoma derived xenografts in immunosuppressed mice. Pretreatment of mouse melanoma cells with 1,25(OH)2D3 resulted in inhibition of migration through extracellular matrix and adherence of the cells to reconstituted basement membrane (Matrigel) type IV collagen and inhibition of the formation of lung metastases, indicating an inhibitory effect on tumor invasion and metastasis.

Skin is an important target site for the actions of vitamin D. Photochemical reactions that produce pre Vitamin D3 (cholecalciferol) only take place in the skin. Keratinocytes and other cells in the skin are capable of synthesizing hormonally active vitamin D metabolite, 1,25(OH)2D3 and there is evidence that 1,25(OH)2D3 can protect skin cells from UV damage (De Haes 2005; Gupta 2007).

Epidemiological evidence for a possible protective influence of sunlight/vitamin D on melanoma risk is suggested by studies showing lower than expected incidence in persons with outdoor occupations, which, according to the authors, could reflect at least in part a level of protection afforded by their greater reserves of vitamin D. The majority of melanomas occur at body sites only receiving intermittent sun exposure, consistent with possibility of inadequate production of

vitamin D as possible cofactor in sites with limited exposure to sun, like trunk and extremities. FokI and BsmI polymorphisms in the VDR, which may influence expression or activity of this protein are associated with an altered melanoma risk (Gandini, 2009). However large epidemiological studies have failed to find an association between dietary vitamin D intake and melanoma incidence (Weinstock 1992; Asgari 2009) and between serum vitamin D levels and melanoma risk (Randerson-Moor 2009).

#### **Added value compared to current knowledge/state of the art initiatives**

Vitamin D levels may have a protective effect on malignant melanoma outcome, as suggested by a reported association of higher 25(OH)D3 serum levels at diagnosis with lower Breslow thickness at diagnosis. Increased 25(OH)D3 serum levels at diagnosis were also independently protective of relapse and death (Newton Bishop, 2009). In the present proposal, we expand these investigations on the potential protective effect of vitamin D on melanoma outcome in a more comprehensive way, because of the following reasons:

1. We will test the protective effect of vitamin D supplementation to melanoma patients (in a placebo controlled and double blind way) against relapse (primary endpoint).
2. We will also immunohistochemically assess the expression of the Vitamin D Receptor (VDR) expression in the primary tumor, and investigate whether VDR immunoreactivity in the primary tumor correlates with relapse (primary endpoint) and melanoma stage at diagnosis. (secondary endpoint)
3. We will monitor increases in vitamin D levels after supplementation (secondary endpoint). This will allow us to assess whether every patient is characterized by the same increase in vitamin D, or whether serum levels following intake depends on genetic variability. Furthermore, this will allow us to monitor compliance to the supplementation.
4. We will correlate vitamin D levels at diagnosis with melanoma site (secondary endpoint) and subtype (secondary endpoint).

#### **1.2. Rationale of the study**

The **rationale** for this project is the need to **improve the outcome of malignant melanoma of the skin**, the most common lethal skin disease, with a large impact in terms of years of life lost. While early stage malignant melanoma (pure radial, early invasive growth phase) can be cured, late stage (metastatic) melanoma decreases the chances of survival markedly because of its resistance to chemotherapy (Balch 2009). Predictors of melanoma progression and survival include histological characteristics of the primary tumor at diagnosis: Breslow thickness, presence of ulceration and number of

mitoses. Improvement of melanoma outcome can be achieved by diagnosing the tumor in an earlier stage (thinner Breslow, absence of mitosis and absence of ulceration) and by decreasing the chance of relapse after surgery of the tumour.

We hypothesize that high dose vitamin D supplementation after surgery of the primary tumor can decrease the chance of relapse, based on previous in vitro and vivo data, which support an anticancer effect of vitamin D.

The active metabolite of vitamin D, 1,25(OH)2D3, demonstrates relevant anti-cancer effects on melanoma cells, not only antiproliferative, prodifferentiating and proapoptotic effects, but also inhibitory effects on tumor invasion and metastasis (Osborne, 2002 and Egan, 2009). These pleiotropic anticancer effects are mediated by the vitamin D receptor (VDR).

Patients in stage IV (metastatic malignant) melanoma show reduced 25(OH)D3 serum levels and a recent study revealed an association of higher 25(OH)D3 serum levels with lower Breslow thickness of the tumor at diagnosis. (2009, Nürnberg, 2009, Newton Bishop 2009)

Serum concentration of 25(OH)D3 is the best indicator of the vitamin D status, which is determined by UVB induced production of vitamin D in the skin, dietary intake and vitamin D supplementation (Sage, 2010). In addition vitamin D status may also be influenced by genetic variants of certain proteins involved in the vitamin D pathway (Wang 2010).

The proposed project will assess whether high dose **vitamin D supplementation after surgery of the primary tumor affects malignant melanoma outcome**. More specifically the following questions will be addressed:

1. Is vitamin D supplementation after diagnosis and surgery of the primary tumor protective against a relapse of malignant melanoma?
2. Does this protective effect on relapse correlate with VDR immunoreactivity in the primary tumor?

### **1.3. Risk-benefit assessment**

In every clinical trial, anticipated benefits need to be weighed against the study associated risks. It is generally agreed that the serum concentration of 25(OH)D3 in normal subjects is the best indicator for vitamin D status and currently a serum concentration below 10 ng/ml (<25/ nmol/L) is considered as vitamin D deficient, and a serum concentration below 20 ng/ml (< 50 nmol/L) as vitamin D insufficient. The optimal level for health is believed to be reached at 30 ng/ml (75 nmol/L), while some individuals may be at risk for toxicity (hypercalcaemia, vomiting, thirst, polyuria, ectopic calcifications) when their 25(OH)D3 levels are in the range of 100-150 ng/ml (or 250-300 nmol/L). Current recommendation for additional vitamin D intake via supplements, in addition to skin synthesis and nutritional intake, is

1000 IU/ d. A good safety profile for this amount has been shown in more than 50 000 subjects over a several year treatment period (Norman and Bouillon, 2010), while doses for chemoprevention studies (colon, prostate and breast cancer) range from 2000 to 4000 IU /day (ClinicalTrials.gov). A recent publication (Lehouck et al, 2012) investigating the effect of vitamin D supplementation on Chronic Obstructive Pulmonary Disease (COPD) on 90 patients in a placebo controlled setting, has shown that a single monthly dose of 100 000 IU, given during a year is safe, is able to increase the 25 (OH)D3 levels in serum, from insufficient levels (<20 ng/ml) to 50 ng/ml, and has no immunosuppressive effects.

The anticipated benefits high dose vitamin D supplementation for study participants are expected better long-term outcomes such as reduced occurrence of relapse and longer relapse free survival period. Given the increased mortality of melanoma patients that progress to a higher stage (Balch et al, 2009) and the patients' burden that is associated with this course (including intensive medical treatment, financial impact and/or inability to work), the ViDMe study offers a valuable adjuvant, low invasive treatment opportunity for participating patients. In view of these facts, the risk benefit ratio seems well balanced in the ViDMe trial so that the benefits outweigh the risks. To account for the described risks, the ViDMe study will assess complications/adverse events associated with vitamin D supplementation. A DSMB Committee will analyze key safety aspects in regular intervals during the ongoing trial to ensure patient safety.

## 2. STUDY OBJECTIVES

### 2.1. Primary objective

The primary endpoint for this study is

- Relapse free survival.

### 2.2. Secondary objective

Secondary efficacy endpoints are:

- Melanoma subtype, as assessed clinically and histologically
- Melanoma site, as clinically recorded
- 25(OH)D3 serum levels at diagnosis and at 6 months intervals
- Stage of melanoma patient at diagnosis according to the 2009 AJCC Melanoma staging and classification

#### **Safety endpoints:**

[figure not shown]
- Incidence and severity of adverse events

### **3. OVERALL DESIGN AND PLAN OF THE STUDY**

#### **3.1. Overview of study flow**

To investigate whether vitamin D supplementation after diagnosis affects malignant melanoma outcome (primary endpoint relapse free survival), stage IB-III patients will be enrolled from fall 2012 to fall 2023. Stage IA patients will not be included in the study because they only have a very small chance to relapse. This double-blind randomized study will comprise 500 patients (stage IB-III). This patient cohort will be randomized in a 1:1 ratio to vitamin D supplementation or placebo. We will also assess the expression of the Vitamin D Receptor (VDR) expression in the primary tumor. A blood sample will be taken for DNA analysis (genetic variability in the vitamin D pathway). We will check 25(OH)D3 serum levels both at diagnosis, and every 6 months until the end of the study. This patient cohort will exist of 3 subgroups (patients diagnosed within 6 or 12 months before start of the study and newly diagnosed patients). Inclusion of previously diagnosed patients will allow us to assess whether delayed supplementation has a similar effect on the relapse free survival rate as immediate supplementation after surgery of the tumor.

In this randomized vitamin D supplemented placebo-controlled trial (both arms), we will assess whether vitamin D supplementation in the follow up period after diagnosis has a protective effect on relapse (primary endpoint) of the malignant melanoma and whether this protective effect correlates with the vitamin D receptor immunoreactivity in the primary tumor.

**Figure 1: Study Flow Chart**

Confidential

### **3.2. Justification of study design**

A previous study has demonstrated the association of higher 25-hydroxyvitamin D3 serum levels with lower Breslow thickness of the tumor at diagnosis (Newton-Bishop, 2009), suggesting a protective effect of higher vitamin D levels on disease progression of cutaneous malignant melanoma.

To further proof the protective effect of Vitamin D supplementation on melanoma disease progression, this study will give high dose vitamin D supplementation to the melanoma patients after surgery of the primary tumor ( which is the current best standard of care), in a placebo controlled and double blind way. The effect of high dose vitamin D supplementation in double blind placebo controlled way will be primarily tested on relapse free survival.

Patients will be randomly assigned in a 1:1 ratio to receive a monthly oral dose of 100 000 IU of vitamin D (1ml of D-Cure) or placebo (1 ml of olive oil). A block randomization method stratified on time of diagnosis (newly diagnosed, 0-6 months or 6-12 months before start of the study) will be used to overcome seasonal influences on baseline characteristics.

We will also assess the expression of the Vitamin D Receptor (VDR) expression in the primary tumor. A blood sample will be taken for DNA analysis (genetic variability in the vitamin D pathway). We will check 25(OH)D3 serum levels both at diagnosis, and every 6 months until the end of the study. If the level of 25(OH)D3 serum is above 80 ng/ml, study drug will be interrupted and during drug free interval the 25(OH)D3 serum levels will be checked every 3 months. When serum 25(OH)D3 falls below 50 ng/ml, study drug is restarted

The patient cohort will exist of 3 subgroups (patients diagnosed within 6 or 12 months before start of the study and newly diagnosed patients). Inclusion of previously diagnosed patients will allow us to assess whether delayed supplementation has a similar effect on the relapse free survival rate as immediate supplementation after surgery of the tumor.

### **3.3. Study population**

#### **3.3.1. Number of patients**

A total of approximately 500 male and female patients will be enrolled in the ViDMe study in this multiple centre study.

### **3.3.2. Inclusion criteria**

1. Older than 18 years and younger than 80 years of age.
2. Histologically proven malignant melanoma, stage IB to III Not participating in other clinical trial.
3. The only treatment for melanoma is surgical treatment.
4. Complete resection of melanoma.
5. Single primary invasive cutaneous melanoma (inclusion within 1 year after diagnosis).
6. Signed ethical committee approved informed consent
7. Serum phosphate and calcium at the entry of the study within normal range of the laboratory reference

### **3.3.3. Exclusion criteria**

1. Pregnant/lactating women or planning on becoming pregnant during the study
2. Known hypersensitivity to vitamin D or its components.
3. Pre-existing renal stone disease or chronic renal disease
4. With eGFR < 30 mL/min/1.73 m^2 or renal dialysis.
5. Liver failure or chronic liver disease with liver enzyme > 2 fold ULN (=upper limit of normal)
6. History of parathyroid disease or granulomatous disease (TBC and sarcoidosis)
7. History of malabsorption syndrome or any medical condition that might interfere with vitamin D absorption.
8. History of other malignancy within the last 5 years except for carcinoma in situ of the cervix or basal cell carcinoma or squamous cell carcinoma of the skin or in situ malignant melanoma.
9. Chronic alcohol abuse.
10. Medical or logistic problems likely to preclude completion of the study.

## 4. STUDY CONDUCT

### 4.1. Schedule of procedures

The schedule of study assessment is listed in Table 1.

**Table 1: Schedule of assessments**

	Screening	Randomization = day 0	Every 3 months FU	Every 6 months FU	End of Study (fall 2023) or Progression/Relapse
Informed Consent	X				
Demographics	X				
Medical History	X				
Melanoma Risk Factors	X				
Sun exposure Behaviour	X				X
Physical Examination	X		x		X
Vitamin D levels		X		X	X
DNA analysis		x			
Safety Laboratory#	X		X	x	X
Concomitant Medications	X	X	X		X
Adverse Event / Endpoint Collection		X	X		X
24 hour urine calcium					X

+

#

# Safety laboratory

Screening and end of study:

Hemoglobin, haematocrit, WBC count with differential, RBC count and platelet count

Renal function (creatinine)

Liver function (AF, ALT, gamma-GT, LDH)

Serum calcium and serum phosphate, and albumin

Every 3 months:

serum calcium, serum phosphate,

Every 6 months

WBC count plus differential

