Therapy	Ampoules of 100 000 IE cholecalciferol (vitamin D3) are prepared by the pharmacist and will be taken orally at a monthly basis. Duration of the treatment: till the end of the study (max 3.5 years) or until relapse. Placebo capsules, consisting of oil preparation will be prepared in the same way. All patients are treated with optimal standard cutaneous melanoma follow-up.
Population	Adult male or female patients with histologically diagnosed stage IB to III cutaneous melanoma are eligible for the trial.
Inclusion Criteria	

1. Older than 18 years and younger than 80 years of age.

2. Histologically proven malignant melanoma, stage IB to III Not participating in other clinical trial.

3. The only treatment for melanoma is surgical treatment.

4. Complete resection of melanoma.

5. Single primary invasive cutaneous melanoma (inclusion within 1 year after diagnosis).

6. Signed ethical committee approved informed consent

7. Serum phosphate and calcium at the entry of the study within normal range of the laboratory reference

Exclusion Criteria	

1. Pregnant/lactating women or planning on becoming pregnant during the study

2. Known hypersensitivity to vitamin D or its components.

3. Pre-existing renal stone disease or chronic renal disease with eGRF < 30 mL/min/1.73 m^2 or renal dialysis.

4. Liver failure or chronic liver disease with liver enzyme > 2 fold ULN (=upper limit of normal)

5. History of parathyroid disease or granulomatous disease (TBC and sarcoidosis)

6. History of malabsorption syndrome or any medical condition that might interfere with vitamin D absorption.

7. History of other malignancy within the last 5 years except for carcinoma in situ of the cervix or basal cell carcinoma or squamous cell carcinoma of the skin or in situ malignant melanoma.

8. Chronic alcohol abuse.

9. Medical or logistic problems likely to preclude completion of the study.

Study duration	Patients are enrolled during a recruitment phase of three years maximum. Study duration for one patient is maximum 3.5 years or until relapse occurs. The DSMB may terminate the study earlier based on safety concerns.

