#### 4.3.4. Clinical laboratory

Blood sampling and sample analysis is performed at the clinical centre. The local investigator is responsible for proper judgment of abnormal blood test results, and is responsible to appropriate patient care following clinically relevant pathological results. Please refer to section 6.4.4 to determine whether an abnormal laboratory value may constitute an adverse event.

The following analysis is to be obtained:

Screening and end of study:

- Hematology: hemoglobin, hematocrit, WBC count with differential, RBC count and platelet count
- Biochemistry and enzymes: serum creatinine, serum calcium, serum phosphate, AF, ALT, gamma GT, LDH

Randomisation (Day 0):

- Baseline serum vitamin D level.
- Bloodsample for DNA analysis

Every 3 months:

- serum calcium
- serum phosphorus
- 25(OH)D3 serum levels, in case of drug interruption when serum 25(OH)D3 levels are > 80 ng/ml

Every 6 months:

- 25(OH)D3 serum levels
- WBC plus differential

End of study: 24 hrs urine calcium

SNP analysis will be performed by the laboratory of [name], VIB

Peripheral blood from study participants will be sampled in K2EDTA tubes.

The samples are coded and only then transferred to VIB. So VIB only has coded information from the patients. Subsequently, tubes will be transferred to the Vesalius Research Center (Leuven) and genomic DNA will be extracted by a standard salting out method and stored at -80 °C until further analysis. Genetic variants affecting VD levels will be genotyped in a blinded manner using iPLEX technology on a MALDI-TOF based MassARRAY Compact Analyser (Sequenom Inc., CA, USA). The Sequenom's iPLEX technology efficiently multiplexes up to 32 different SNP's in one PCR reaction, thereby providing rapid and accurate SNP genotypes at an affordable price. Only samples for which ≥ 80% SNPs have succeeded will be considered for further analysis. SNPs with a call rate < 98% will be re-designed and genotyped again to reach success rates close to 100%. At least 5% of the samples will be genotyped in duplicate, to prove accuracy of the genotyping protocol. We expect that approximately 2 Sequenom assays will have to be applied on the DNA of participating individuals to cover all 19 SNPs. Multiple Single Nucleotide Polymorphisms (SNPs) have been reported to affect VD signaling.

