### 6.1.2. Serious and non-serious adverse events

All AEs fall into either the category “non-serious” or “serious”. A serious adverse event (SAE) is any untoward medical occurrence that at any dose:

- Results in death
- Is life-threatening
- Requires inpatient hospitalisation or prolongation of existing hospitalisation
- Results in persistent or significant disability or incapacity
- Is a congenital anomaly or birth defect
- Is an important medical event

A non-serious adverse event is any untoward medical occurrence that does not fulfil any of the criteria listed above.

Adverse events with respect to abnormal assay results and precautionary safety procedures to be taken:

- Clinical significant hypercalcemia: defined as 2 independent measurements (2 different laboratories), above the reference value; action taken: end of study
- HypervitaminoseD: defined as 25(OH)D3 > 80 ng/ml; action taken: discontinue study drug and restart monthly treatment with study drug when 25(OH)D3 falls below 50 ng/ml on 3 monthly monitoring .
- Hypovitaminose D:
  - \* Serum 25(OH)D3 < 10 ng/ml at baseline; action taken: supplementation of extra vitamin (D-cure): 25000IU / month,
  - \* Serum 25(OH)D3 < 10 ng/ml at 6 months or later; action taken: end-of-study
  - \* Serum 25(OH)D3 > 10 ng/ml and < 20 ng/ml at baseline: supplementation of extra vitaminD (D-cure): 25000IU/month
  - \* Serum 25(OH)D3 > 10 ng/ml and < 20 ng/ml at 6 months or later: supplementation of extra vitaminD (D-cure): 25000IU/month
- Hypophosphatemia: < 1.5 mg/dl: further investigation
- Hyperphosphatemia: > 6mg/dl: further investigation

*Clarification of the difference in meaning between “severe” and “serious”*

Confidential

#

page 40 of 52

The term “severe” is often used to describe the intensity (severity) of a specific event (see next section below); the event itself, however, may be of relatively minor medical significance (such as severe headache). This is not the same as “serious”, which is based on the outcome or action criteria usually associated with events that pose a threat to life or functioning. Seriousness (not severity) serves as a guide for defining regulatory reporting obligations.

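### No scheduled test measures kidney function during treatment: creatinine is taken only at screening and at end of study or relapse, across up to 42 months of monthly 100 000 IU vitamin D

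*Combined protocol and SAP*

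**What the plan says.** The Safety laboratory footnote to Table 1 (section 4.1) places "Renal function (creatinine" in the set for screening and end of study. The 3-monthly set is calcium and phosphate. The 6-monthly set is white cells with differential.

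Section 4.3.4 agrees. Its list for screening and end of study reads "Biochemistry and enzymes: serum creatinine, serum calcium, serum phosphate, AF, ALT, gamma GT, LDH". It adds 25(OH)D3 every 6 months, and every 3 months while study drug is interrupted. The only urine test comes last: "End of study: 24 hrs urine calcium". The same section states: "The local investigator is responsible for proper judgment of abnormal blood test results".

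Table 1 heads its last column as end of study or progression/relapse.

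The synopsis excludes "Pre-existing renal stone disease or chronic renal disease with eGRF" below 30 mL/min/1.73 m², or dialysis. Treatment is 100 000 IU monthly for at most 3.5 years or until relapse.

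The laboratory action rules in section 6.1.2 cover three analytes:
- Calcium: "Clinical significant hypercalcemia: defined as 2 independent measurements (2 different laboratories), above the reference value; action taken: end of study".
- 25(OH)D3: study drug is interrupted above 80 ng/ml and restarted below 50 ng/ml, and low values lead to a supplement or withdrawal.
- Phosphate: limits at both ends, for example "Hyperphosphatemia: > 6mg/dl: further investigation".

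Neither section 6.1.2 nor the list of reportable values in section 6.4.4 has a creatinine or eGFR item.

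**The concern.** The protocol treats the kidney as relevant at entry and then has no scheduled look at it until treatment is over. A patient without symptoms whose eGFR fell below the entry limit during treatment could go on receiving study drug, unless calcium, phosphate or 25(OH)D3 went out of range or someone ordered a test outside the schedule. The end-of-study value comes too late to change that patient's dosing.

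The same gap limits the DSMB. The only scheduled post-baseline creatinine values it could see come from patients who have already finished or relapsed.

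Exposure is also longer than in the study of this monthly dose that section 1.3 cites, which had 90 patients treated for one year. What is at stake is participant safety and the quality of the safety data, not the efficacy result.

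**Working it through.** The plan gives no figure of its own on this point. The check compares the schedule with the action rules and then counts tests.

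**Schedule and rules side by side**

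| Measure | When scheduled | Action rule in 6.1.2 |
|---|---|---|
| Calcium | Screening, every 3 months, end | Withdrawal if confirmed high |
| Phosphate | Screening, every 3 months, end | Investigate outside limits |
| 25(OH)D3 | Day 0, every 6 months, end | Interrupt above 80 ng/ml, restart below 50 ng/ml; supplement or withdraw if low |
| 24-hour urine calcium | End | None |
| Creatinine | Screening, end or relapse | None |

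Table 1 also marks the safety laboratory at the 3- and 6-monthly visits. The footnote defines what is drawn at those visits, and creatinine is not in either set.

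**Exposure and gap, full-term patient** (maximum 3.5 years, synopsis)
- Months: 3.5 × 12 = 42, so 42 monthly doses.
- Total dose in the active arm: 42 × 100 000 = 4.2 million IU.
- Creatinine tests between first dose and final visit: 0. The whole 42-month treatment period lies between the two scheduled tests.
- With 6-monthly testing: months 6, 12, 18, 24, 30 and 36, which is 6 tests, and a longest gap of 6 months.
- For comparison, 3-monthly testing would give 13 interim tests (months 3 to 39) and yearly testing 3.

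**Number of added assays at 6-monthly testing** (500 patients in total, sections 3.1 and 3.3.1; relapse ignored, so each figure is on the high side for its scenario)
1. Upper bound, everyone followed 42 months: 6 × 500 = 3,000.
2. Enrolment window in sections 3.1, 4.2 and 4.3.9 (fall 2012 to fall 2023, 132 months), with follow-up ending in fall 2023 and capped at 42 months. Uniform accrual is assumed. The first 132 − 42 = 90 months of recruits have 6 interim tests each. The last 42 months of recruits have 0 to 6, mean 3. Mean per patient: (90 × 6 + 42 × 3) / 132 = 666 / 132 = 5.05. Assays: 5.05 × 500 ≈ 2,500.
3. Sample-size plan in section 7.1 (3 years of recruitment, 3.5 years in total). Uniform accrual is assumed, so follow-up runs from 6 to 42 months. Mean per patient: (1 + 2 + 3 + 4 + 5 + 6) / 6 = 3.5. Assays: 3.5 × 500 = 1,750.

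Scenario 2 follows the enrolment dates in the current text; scenario 3 follows the recruitment period behind the power statement. These counts describe the schedule and its cost. They do not measure risk. The documents give no rate of renal decline on treatment, and with 1:1 allocation half the patients take placebo.

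**The case against.** The strongest reply is that the plan monitors the hazard it names. Sections 1.1 and 1.3 describe vitamin D toxicity as hypercalcaemia and its consequences, and place the risk at 25(OH)D3 levels of 100–150 ng/ml. Study drug is interrupted above 80 ng/ml, which leaves a margin. Calcium and phosphate are checked every 3 months, and confirmed hypercalcaemia ends participation. An unblinded DSMB reviews complications of the high dose, initially every three months (section 8.2.2). The investigator may end participation on medical grounds (section 4.3.8) and must ensure care for clinically significant laboratory values (section 6.2). The dose is not extreme beside the chemoprevention range of 2000–4000 IU/day in section 1.3: 100 000 × 12 / 365 ≈ 3,290 IU/day, or 125 000 × 12 / 365 ≈ 4,110 IU/day with the 25 000 IU supplement in section 6.1.2.

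Most of this stands, and it is why the point is an improvement and not a serious failing. What remains is that none of these safeguards measures kidney function. The duty to judge abnormal results depends on a test having been done, and the DSMB cannot review renal values that were not collected. The chemoprevention range does not close the gap either, because section 1.3 does not say how those studies monitored the kidney or how long they ran.

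It can also be said that an entry criterion does not imply a stopping rule. That is correct: nothing in the documents establishes an eGFR of 30 as the right limit for holding drug.

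**Conclusion.** The point holds as a low-cost safety improvement that the sponsor should make. Both places that list the laboratory tests agree on the timing of creatinine, so the gap is a feature of the schedule and not a reading problem. Its size is up to 42 months without a scheduled renal test, for a patient who neither relapses nor leaves early. Patients who relapse reach the final laboratory set sooner. Power and the primary analysis are unaffected.

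Three stronger readings are tempting, and the documents do not support them:
- A reader might infer that the regimen is damaging kidneys, or that patients are unprotected. The documents give no renal event rate, and the intoxication rules are substantive.
- Section 3.3.3 puts "Pre-existing renal stone disease or chronic renal disease" and the eGFR limit in separate numbered items, so a reader might infer that all chronic renal disease is barred. The second item begins mid-phrase and the synopsis gives the text as one criterion, so a list-splitting slip is the natural explanation. The point does not rest on it.
- Albumin is not in the 3-monthly sample, so a reader might infer that the hypercalcaemia rule is unsound. That would need the calcium to be total calcium, and the documents do not say which form is measured.

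**What to change.** 1. In the Safety laboratory footnote to Table 1 and in section 4.3.4, add serum creatinine with eGFR (formula stated) to the existing 6-monthly blood draw.
2. In section 6.1.2, add a rule that an eGFR below a stated limit, confirmed on a repeat sample, leads to holding study drug and review, with a restart criterion. The entry limit of 30 mL/min/1.73 m² is a reasonable default, but the sponsor should set and justify the value.
3. Report eGFR by arm to the DSMB.

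The cost is at most 3,000 creatinine assays: about 2,500 with uniform accrual over the 2012–2023 window, or about 1,750 under the section 7.1 recruitment plan. No visit or routine blood draw is added. There will be some confirmatory repeat samples, some incidental abnormal values to handle, a few eCRF fields, and a short amendment to Table 1 and sections 4.3.4 and 6.1.2.
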